**Title: Mechanistic Studies on Video-guided Acupuncture Imagery Treatment of Knee Pain**

**Clinical trial ID: NCT03261505**

**Date: 11/8/2023**

## Statistical plan for primary outcome

**Primary outcome:** fMRI signal changes evoked by the different interventions.

**fMRI data acquisition** All brain imaging was performed with a 3-axis gradient head coil in a 3 Tesla Siemens MRI System equipped for echo planar imaging. A high-resolution 3D MPRAGE sequence was collected for anatomic localization of significant signal changes. Functional MRI images were acquired using a gradient echo T2\*-weighted pulse sequence (TR/TE = 2000/30ms, flip angle = 90°, FOV = 192x192 mm, 48 AC-PC aligned slices, slice thickness = 3.0 mm with 0.6 mm inter-slice gap, 90 image volumes per slice, matrix = 96x96).

**Data analysis:** SPM 12 was applied to investigate the brain responses to different interactions. Preprocessing included co-registration, motion correction, normalization to MNI stereotactic space, and spatial smoothing with an 8 mm Gaussian kernel. For each subject, the contrast between manipulation and no manipulation during acupuncture and sham acupuncture was calculated using a general linear model. The same procedure was followed for V-GAIT and control touching. For V-GAIT, the contrast was between watching/imagining needle manipulation vs. no manipulation, and for the control, contrast was between cotton swab touching vs. no manipulation.

Group analysis was performed using a random-effects model. A one-sample t-test was performed to compare the fMRI signal changes during manipulation vs. no manipulation within each treatment. Then, ANOVA was used to compare the differences among treatment groups. Thresholds of  $p < 0.005$  and  $p < 0.05$  small volume corrected were applied for the region of interest (ROI). Thresholds of  $p < 0.005$  uncorrected and  $p < 0.05$  Family-wise Error (FWE) corrected were used for non-ROI. Based on previous studies and our hypothesis, the ROIs included: the cingulate cortex, insula, primary and secondary somatosensory cortex, dorsal lateral prefrontal cortex, medial prefrontal cortex, inferior parietal lobule, and periaqueductal grey (PAG).

Some subjects were excluded from the MRI data analysis due to the poor quality of the MRI signal due to head movement during the MRI scan. The number of subjects used in this analysis was: 24 for real acupuncture, 25 for sham acupuncture, 23 V-GAIT, 26 V-GAIT control.

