Randomization Patients who pass the screening will be randomized into one of the four groups using a centrally generated, variable-sized block design.

Endpoints

Primary outcomes

The primary outcome will be blood oxygen level (BOLD) response (fMRI signal) differences evoked by V-GAIT and V-GAIT control.

Secondary outcomes

Secondary outcomes will include 1) PAG resting state functional connectivity differences before and after one month of treatment; 2) KOOS Score [30] (we will focus on KOOS pain subscale score based on previous studies [2, 31-33]) and other clinical outcomes (see below for details); and 3) QST [1, 34]. All clinical outcomes will be measured at baseline and after the last treatment.

PAG-ACC/mPFC resting state functional connectivity will be assessed by calculating Pearson's correlation between the fMRI scan time courses of the PAG and ACC / MPFC using the CONN toolbox [35], while the subject is resting in the fMRI scanner prior to beginning the treatment and again immediately after the treatment. In short, preprocessing of resting state fMRI data will

include co-registration, motion correction, normalization to MNI stereotactic space, and spatial smoothing with an 8 mm Gaussian kernel. Functional connectivity analysis for individual subjects will be carried out using the PAG as a seed. Specifically, the average time course of the PAG will be obtained and correlation analysis will be performed in a voxel-wise way to generate a functional connectivity map for PAG. The resulting correlation coefficient map will be converted into a Fisher-Z map using Fisher's r-to-z transformation to improve the normality, and then will be entered into the group analysis. Group analysis will be performed using CONN toolbox [35]. A full factorial module in SPM 12 will be performed to compare the PAG rsFC changes before and after about one month of VGAIT, VGAIT control, real and sham treatments.

Blindness During data acquisition, all study personnel except the administering acupuncturist will be blinded with respect to treatment conditions. Patients will also be blind to acupuncture modality (real or sham) they receive till end of the study, a study investigator will debrief the subject and explain the rational of blindness.

Experimental procedure

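### The protocol makes V-GAIT and its control the primary outcome; the SAP's primary-outcome plan covers all four interventions and designates no group contrast between those two arms

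*SAP*

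**What the plan says.** Protocol, section V, Endpoints, Primary outcomes: "The primary outcome will be blood oxygen level (BOLD) response (fMRI signal) differences evoked by V-GAIT and V-GAIT control".

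SAP, Statistical plan for primary outcome: the primary outcome is "fMRI signal changes evoked by the different interventions". The SAP's Data analysis text then gives three steps.

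- Subject level: "For each subject, the contrast between manipulation and no manipulation during acupuncture and sham acupuncture was calculated using a general linear model". The video arms are treated the same way: "For V-GAIT, the contrast was between watching/imagining needle manipulation vs. no manipulation", with swab touching against no manipulation for the control.
- Within arm: "A one-sample t-test was performed to compare the fMRI signal changes during manipulation vs. no manipulation within each treatment".
- Between groups: "Then, ANOVA was used to compare the differences among treatment groups".

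It closes with the analysed numbers: "The number of subjects used in this analysis was: 24 for real acupuncture, 25 for sham acupuncture, 23 V-GAIT, 26 V-GAIT control".

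The SAP names no group contrast, follow-up procedure or order of testing for the ANOVA. Its small-volume and family-wise thresholds concern voxels and regions. None is stated across group comparisons.

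**The concern.** The two documents do not give the same primary outcome. The protocol singles out one pair of arms. The SAP, in the section meant to say how that outcome is analysed, speaks of the interventions in general and names no pair.

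The V-GAIT and control contrasts that the SAP does spell out are calculated within each subject, so they do not compare the two arms. The only between-group step is an ANOVA across four groups.

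What is at stake is which result counts as primary. An omnibus F, any of the other pairwise contrasts, or a significant map within one arm would each fit the SAP's description. Each can occur with no difference between V-GAIT and its control.

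**Working it through.** **1. The definitions side by side**

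| | Protocol, Endpoints | SAP, primary-outcome plan |
|---|---|---|
| Conditions | V-GAIT and V-GAIT control | The interventions in general; all four analysed |
| Quantity | Differences in BOLD response | Changes in fMRI signal |
| Group contrast named | The pair is named | None |

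**2. Does any SAP step supply the protocol's comparison?**

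- The subject-level contrasts give one map per person. No arms are compared.
- The one-sample t-tests ask whether the mean signal in one arm differs from zero. A significant map in one arm and not in the other is not a test of their difference.
- The ANOVA includes both arms. If it means the omnibus F, it tests whether any of the four means differ. If it means a four-group model from which contrasts are drawn, the protocol's comparison is one of 4 × 3 / 2 = 6 pairs. The SAP does not say which is meant.

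The protocol's plan for resting-state connectivity is a hint for the second meaning: "A full factorial module in SPM 12 will be performed to compare the PAG rsFC changes". That sentence concerns a secondary outcome and names no primary contrast either.

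**3. How far the omnibus F can depart from the protocol's question**

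Neither document gives an effect size, an SD or a power figure, so there is no stated calculation to reproduce. What follows is an illustration on assumptions: a single ROI mean per subject, SD 1, and one arm differing by d. It does not model voxelwise inference with small-volume correction.

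Inputs from the SAP: n = 24 real, 25 sham, 23 V-GAIT, 26 control. N = 24 + 25 + 23 + 26 = 98. Degrees of freedom are 3 and 98 − 4 = 94.

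Formula: power = P[F′(3, 94, λ) > critical value], where λ = Σ nᵢ(μᵢ − μ̄)² and μ̄ is the weighted mean.

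Only real acupuncture differs, d = 0.8, with V-GAIT equal to its control:

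- μ̄ = 24 × 0.8 / 98 = 0.196
- λ = 24 × (0.8 − 0.196)² + 74 × 0.196² = 8.76 + 2.84 = 11.60
- Alpha 0.05, critical value 2.70: power 0.809
- Alpha 0.005, critical value 4.56: power 0.501

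Range over the assumed difference, using λ = d² × 24 × 74 / 98 = 18.12 d²:

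| d (real acupuncture only) | λ | Alpha 0.05 | Alpha 0.005 |
|---|---|---|---|
| 0.5 | 4.53 | 39% | 12% |
| 0.8 | 11.60 | 81% | 50% |
| 1.0 | 18.12 | 95% | 79% |

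For comparison, if only V-GAIT differs by 0.8, then λ = 0.64 × 23 × 75 / 98 = 11.27 and the power at alpha 0.05 is 0.796. The F test gives nearly the same chance of rejection whether V-GAIT differs from its control or not. In the first case the rejection is correct, but it answers a different question.

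**The case against.** **The four-arm analysis is within scope.** Aim 1 and Hypothesis 1.1 compare all four conditions, and the ANOVA contains both video arms. This stands. It rules out saying that the comparison was removed or that a four-arm analysis is improper. It does not settle which result is primary, because the protocol's endpoint definition picks out one pair.

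**The protocol's sentence is not airtight.** It never says that the difference is between the two arms. It could be read as the on/off signal difference that each condition evokes, which the SAP's subject-level contrasts measure. The between-arm reading is the more natural one, and the mismatch of two conditions against four remains on either reading.

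**The figures do not describe the SAP's procedure.** This also stands. The SAP works voxelwise at 0.005 with small-volume correction, and the 81% falls to 50% at alpha 0.005 even on the simple ROI-mean model. The defect is in the text, and the figures only illustrate it.

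Three stronger readings go beyond the documents:

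- *The primary outcome was switched after the results were seen.* The SAP is dated 11/8/2023, after the protocol (02/28/23), is written in the past tense and reports numbers after exclusions. The documents therefore do not show that the wider wording came before the results. Nor do they show that it came after, or that it is more than loose wording.
- *Six pairwise tests inflate the false-positive rate.* If all six are run unadjusted at 0.05 with no arm differing, simulation on one ROI mean gives at least one significant result about 20% of the time (2.5% at 0.005). That supposes pairwise tests with no gate. If they follow only a significant F, the figure under the same null is about 5%. The SAP states neither procedure.
- *The protocol's contrast was not computed or not reported.* Nothing in the documents shows this.

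**Conclusion.** The point holds as an inconsistency in the definition of the primary outcome. The protocol names V-GAIT and its control. The SAP names the interventions in general and designates no group contrast between those two arms. Nothing else in either document closes the gap.

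The consequence is ambiguity about which result is primary, not a loss of power and not a demonstrated error in the analysis. On the stated assumptions, an omnibus F would reject about 81% of the time at alpha 0.05, or 50% at 0.005, in a case where the answer to the protocol's question is no difference. Those percentages depend on the assumed 0.8 SD.

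Because the gap concerns the primary endpoint, it should be closed before any fMRI result is described as primary. Confidence in the textual finding is high.

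**What to change.** 1. Reconcile the definitions. Name V-GAIT minus V-GAIT control, estimated in the four-group model, as the primary between-group contrast. Test it in the SAP's stated ROIs at its small-volume-corrected threshold, and report it for every ROI whatever the result.
2. Label the four-group ANOVA and the other pairwise contrasts secondary, and the within-arm maps descriptive.
3. If the primary outcome was broadened on purpose, say so. State when, why, and whether this was before or after the fMRI results were seen. Still report V-GAIT minus control as the primary outcome that the protocol specified.

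The cost is SAP wording, one contrast in a model already fitted, and a short disclosure. The small downside is that results outside this contrast can no longer be called primary.

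Two limits remain. Naming the contrast now does not make it prospectively specified in the SAP; its prior basis is the protocol's endpoint. And the SAP lists eight regions (counting primary and secondary somatosensory cortex separately) with no rule across them, which is why the contrast should be shown for all of them.

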As an invasive treatment, acupuncture involves needle insertion and manipulation. Literature suggests that *deqi* (sensations evoked by acupuncture needle manipulation such as soreness, aching, and dull pain) are crucial for treatment effects [24-26]. To the extent that these acupuncture sensations can be elicited by watching a video of acupuncture treatment and imagining the treatment, one would expect that brain activity changes would be produced that overlap with those changes produced by real acupuncture needle manipulation. Indeed, this has been demonstrated by a previous brain imaging study in which investigators found that visualizing images of acupuncture needle stimulation [27] produced overlapping fMRI signal changes in the brain at the anterior insula (AI), middle cingulate cortex (MCC)/dorsal anterior cingulate cortex (dACC), and periaqueductal grey (PAG).

Taken together, these findings provide a solid foundation for VGAIT. Most importantly, applying powerful brain imaging tools to explore the neuroscience of mind-body interaction and then testing its treatment effect in a patient population may elucidate how the mind can alter perception [11] and thereby reshape pain experience to achieve a therapeutic effect.

II. SPECIFIC AIMS

The aim of this proposal is to investigate brain response and connectivity changes evoked by video-guided acupuncture imagery treatment (VGAIT) and verum and sham acupuncture in patient populations to elucidate the underlying brain mechanisms of mind-body interaction, imagery, and acupuncture.

Specific Aim 1: Characterize and compare the brain response evoked by VGAIT, a VGAIT control condition, and real and sham acupuncture in chronic pain patients.

Hypothesis 1.1 VGAIT and real acupuncture will produce overlapping fMRI signal increases in AI, MCC/dACC, and PAG as compared to control and sham acupuncture. Real acupuncture will produce greater fMRI signal increases at primary somatosensory cortex (S1) compared to VGAIT in OA patients.

Hypothesis 1.2: Pain intensity ratings of the OA patients will be reduced after about one month of VGAIT and real acupuncture treatment; fMRI signal increases at AI, MCC/dACC, and PAG evoked by treatment will be associated with knee pain intensity reduction after about one month treatment.

Specific Aim 2: Characterize and compare the modulation effects of different treatments on resting state functional connectivity (rsFC) in chronic pain patients.

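### The SAP's only between-arm test is a direction-free four-arm ANOVA, not linked to the within-arm maps, so it cannot separate a V-GAIT increase from a fall in the control arm

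*SAP*

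**What the plan says.** - **Hypothesis** (Protocol, II. Specific Aims, Hypothesis 1.1): "VGAIT and real acupuncture will produce overlapping fMRI signal increases in AI, MCC/dACC, and PAG as compared to control and sham acupuncture". This states a direction.
- **Primary outcome, protocol** (V. Study Procedures, Endpoints): "The primary outcome will be blood oxygen level (BOLD) response (fMRI signal) differences evoked by V-GAIT and V-GAIT control". This names the comparison but no direction.
- **Primary outcome, SAP** (Statistical plan for primary outcome): "fMRI signal changes evoked by the different interventions". This has no direction and covers all arms.
- **Subject-level contrasts** (SAP, Data analysis): "For V-GAIT, the contrast was between watching/imagining needle manipulation vs. no manipulation", and "for the control, contrast was between cotton swab touching vs. no manipulation". Both are signed differences and can be negative.
- **Within-arm test** (same paragraphs): "A one-sample t-test was performed to compare the fMRI signal changes during manipulation vs. no manipulation within each treatment".
- **Between-arm test** (the next sentence): "Then, ANOVA was used to compare the differences among treatment groups".

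The SAP does not give the sidedness of either test. It names no pairwise contrast and has no masking or conjunction rule joining the two steps. It also states no rule for when Hypothesis 1.1 is supported.

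**The concern.** The arms are compared on signed quantities with a test that ignores sign. V-GAIT can differ from its control in three ways: V-GAIT rises, the control falls while V-GAIT does nothing, or V-GAIT falls. Only the first agrees with Hypothesis 1.1, and the ANOVA can be significant under all three. A significant four-arm F need not involve the V-GAIT versus control pair at all.

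At stake is the trial's mechanistic conclusion, that imagined needling activates regions such as the insula, cingulate and PAG. The SAP already computes a map that would help separate the three cases, the one-sample result in the V-GAIT arm. It does not say how that map and the ANOVA are to be read together.

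**Working it through.** The documents give no effect size, SD or power figure for the fMRI outcome, so there is no planned figure to reproduce. The following is an illustration at a single location.

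**Inputs**
- Analysed patients (SAP, last paragraph): 23 V-GAIT, 26 V-GAIT control, 24 real, 25 sham; total 98.
- Threshold: p<0.005, the SAP's voxel-level ROI figure, taken here as two-sided because sidedness is not stated. The small-volume correction is not modelled.
- Assumed: contrast SD of 1 in each arm; true V-GAIT response 0; control fall of 0.6, 0.8 or 1.0 SD.

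**Step 1. Pairwise V-GAIT versus control test**

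SE = √(1/23 + 1/26) = √(0.04348 + 0.03846) = 0.2863. Degrees of freedom = 23 + 26 − 2 = 47. The critical t at two-sided 0.005 is 2.946. The noncentrality is the fall divided by SE, and the noncentral t distribution gives the chance of significance. The last column, from simulation, adds a positive V-GAIT one-sample t at one-sided p<0.05.

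| Control fall (SD) | Noncentrality | Significant | Significant and V-GAIT one-sample increase |
|---|---|---|---|
| 0.6 | 2.10 | 21% | about 4% |
| 0.8 | 2.79 | 45% | about 5% |
| 1.0 | 3.49 | 70% | about 5% |

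The last column cannot exceed about 5%, because V-GAIT truly does nothing and the added test is one-sided at 5%. At a looser two-sided 0.05 the third column would be 54%, 78% and 93%, and the last would stay at 5%.

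**Step 2. The four-arm F that the SAP names**

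Degrees of freedom are 3 and 98 − 4 = 94; the other arms are at 0 and the threshold is 0.005. The F is significant in about 53% of simulated trials when only the control falls by 0.8 SD. It is significant in about 48% when V-GAIT itself falls by 0.8 SD, the opposite of the hypothesis.

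**Step 3. Direction alone is not enough**

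A one-sided V-GAIT > control contrast at p<0.005, using the pooled ANOVA error, removes the reversed case. It remains significant in 20%, 57%, 80% and 94% of runs for control falls of 0.5, 0.8, 1.0 and 1.2 SD with no V-GAIT response. The link to the within-arm result is what separates the cases.

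**Step 4. Price of the link**

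The true V-GAIT minus control difference is held at 0.8 SD. Entries are power of the two-sided contrast alone → with the V-GAIT one-sample increase (one-sided p<0.05) also required.

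| V-GAIT / control (SD) | Contrast at 0.05 | Contrast at 0.005 |
|---|---|---|
| +0.8 / 0 | 78% → 78% (loss of about 0.2 points) | 45% → 45% |
| +0.5 / −0.3 | 78% → 67% | 45% → 43% |
| +0.3 / −0.5 | 78% → 39% | 45% → 31% |

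**The case against.** The strongest reply is that the SAP already tests activation. The sentence just before the ANOVA describes a signed one-sample test in each arm, and anyone following the plan would have a V-GAIT map showing whether the signal rose. That is correct, and it limits the point to the missing link between the two steps.

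A reader might infer that the SAP treats any arm difference as V-GAIT-evoked activation. The documents do not support that: the SAP contains no such rule, and no success rule at all. A reader might also infer that the primary outcome has two conflicting definitions of direction. That does not follow either. Hypothesis 1.1 is a hypothesis, the Endpoints section defines the outcome, and a non-directional test of a directional hypothesis is ordinary practice. Hypothesis 1.1 is also partly relative, since the increases are compared with control and sham. The between-arm comparison is therefore needed; alone, it is insufficient.

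Two further objections stand. Nothing in the documents suggests that cotton-swab touching lowers the signal in these regions, so the size of the control fall is purely assumed. And requiring a within-arm increase can discard real V-GAIT effects, as Step 4 shows.

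These objections do not remove the gap. The protocol makes one pair of arms primary and predicts a direction, while the SAP names neither that pair nor a sign in its between-arm test.

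**Conclusion.** The point holds in limited form. The between-arm analysis does not isolate the protocol's primary comparison or its hypothesised direction, and nothing ties it to the within-arm V-GAIT result. A significant ANOVA is therefore not, by itself, evidence for Hypothesis 1.1.

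The 21%, 45% and 70% figures rest on one location, SD 1, no V-GAIT response, the assumed control falls and a two-sided reading of p<0.005. They show what the test can do, not what happened in this trial. That the between-arm test alone cannot tell a V-GAIT rise from a control fall does not depend on the threshold or the effect size. The point merits a change because the better analysis uses maps already computed.

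**What to change.** 1. Keep the protocol's primary outcome, the V-GAIT versus V-GAIT control difference.
2. After the ANOVA, test the signed V-GAIT minus V-GAIT control contrast and, likewise, real minus sham. State the sidedness.
3. At every significant peak, report each arm's mean contrast with its sign.
4. Claim support for Hypothesis 1.1 on V-GAIT only where V-GAIT > control coincides with a positive V-GAIT one-sample result (for example one-sided p<0.05). Describe other differences as control-driven or reversed.
5. Report the unmasked contrast alongside.
6. The SAP is dated 11/8/2023, is written in the past tense and reports exclusions already made. Label the rule post hoc unless it was fixed before the analysis.

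**Cost.** No new data; it needs SAP wording and re-thresholding of existing maps. Almost no power is lost when the control is flat. The loss is material when a modest V-GAIT rise is combined with a control fall (Step 4), which is why item 5 is needed. Some control-driven differences will no longer count as support for Hypothesis 1.1.

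### The SAP sets a 5% small-volume-corrected threshold for eight brain regions but no search volume, correction across regions, primary region or success rule, so the error rate of the primary contrast is not fixed

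*SAP*

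**What the plan says.** The SAP (Statistical plan for primary outcome) defines the outcome as "fMRI signal changes evoked by the different interventions" and names no contrast. After within-group tests, "Then, ANOVA was used to compare the differences among treatment groups". The listed regions get p < 0.005 and p < 0.05 thresholds, "small volume corrected were applied for the region of interest (ROI"). Voxels outside them get p < 0.005 uncorrected and a 5% family-wise threshold.

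The list is introduced thus: "Based on previous studies and our hypothesis, the ROIs included: the cingulate cortex, insula, primary and secondary somatosensory cortex". It continues with dorsolateral and medial prefrontal cortex, inferior parietal lobule and PAG, which makes eight regions if S1 and S2 are counted separately. The SAP is written in the past tense and reports final numbers: "The number of subjects used in this analysis was: 24 for real acupuncture, 25 for sham acupuncture, 23 V-GAIT, 26 V-GAIT control".

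The protocol (Study Procedures, Endpoints) makes the primary outcome the BOLD difference between V-GAIT and V-GAIT control, without naming a region. Regions appear in Hypothesis 1.1 (Specific Aims): "VGAIT and real acupuncture will produce overlapping fMRI signal increases in AI, MCC/dACC, and PAG as compared to control and sham acupuncture". S1 is tied to a different comparison: "Real acupuncture will produce greater fMRI signal increases at primary somatosensory cortex (S1) compared to VGAIT in OA patients". S2 appears only in the background section as an activation site, and MPFC appears in the protocol only in connection with connectivity. Dorsolateral prefrontal cortex and inferior parietal lobule do not appear in the protocol.

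**The concern.** Small-volume correction controls the error rate inside whatever volume is searched. Run separately in eight regions at 5% each, it controls each region but not the set. The family-wise correction in the SAP is stated for voxels outside the regions, so it does not fill this gap. Hypothesis 1.1 narrows the regions for V-GAIT against its control to three, but it does not rank them or say whether one positive region is enough or all three are needed.

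The primary result is therefore open to several readings with very different error rates. A reader of the report cannot tell which one applies, or which regional findings are confirmatory.

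**Working it through.** The documents give no overall error rate, power or sample-size figure for this outcome, so there is none to reproduce.

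**Inputs from the documents.** Threshold 0.05 per region; k = 8 regions (SAP) or 3 (Hypothesis 1.1); arms of 24, 25, 23 and 26, total 98, so the ANOVA error has 98 - 4 = 94 degrees of freedom.

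**Assumptions.** One summary statistic per region; equal correlation ρ between regions; V-GAIT equal to its control in every region. Values of ρ and the effect sizes below are assumed.

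**1. Per region, any one counts, no ANOVA required.**

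Independent regions: 1 - 0.95^8 = 1 - 0.663 = 33.7%.

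Correlated regions, one-sided: 1 - E[Φ((c - √ρ·G)/√(1-ρ))^k], with G standard normal and c = 1.645. The two-sided form uses c = 1.960 and the probability of lying between -c and c.

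| Regions | ρ = 0 | ρ = 0.5 (one-/two-sided) | ρ = 0.9 (one-/two-sided) |
|---|---|---|---|
| 8, each at 0.05 | 33.7% | 21.9% / 25.0% | 10.9% / 11.9% |
| 3, each at 0.05 | 14.3% | 11.8% / 12.5% | 8.0% / 8.4% |
| 3, smallest p at 0.05/3 = 0.0167 | 4.9% | 4.3% / 4.5% | 2.9% / 3.0% |
| 8, smallest p at 0.05/8 = 0.00625 | 4.9% | 3.7% / 4.0% | 1.7% / 1.8% |

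**2. Same, but a significant four-group ANOVA in that region is required first.** Simulated subjects in eight regions, F and two-sided t each at 0.05:

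| Truth | ρ = 0 | ρ = 0.5 | ρ = 0.9 |
|---|---|---|---|
| All four arms equal | 14% | 11% | 5% |
| Real acupuncture differs by 0.8 SD in one region, other arms equal | 17% | 13% | 7% |

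The second row uses one region because S1 is the only place where the protocol predicts real acupuncture above VGAIT.

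**3. One combined mask.** A single one-directional or two-sided test has a 5% error rate. If both directions are tested at 0.05 each, it is up to 0.05 + 0.05 = 10%. If a hit in the search outside the regions also counts as success, it is 1 - 0.95^2 = 9.75% with independent searches. These are the rates for either departure alone.

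**4. All three hypothesised regions required, each at 0.05.** With no effect anywhere, the rate is 0.05^3 = 0.01% for independent regions, rising to about 2.3-2.5% at ρ = 0.9. It cannot exceed 5% even if two of the three regions truly respond.

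**5. Price of correction.** For one two-sided test of 23 against 26, the standard error is √(1/23 + 1/26) = 0.286 SD. The difference detectable with 80% power is about (critical t + 0.846) × 0.286:

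- at 0.05: (1.986 + 0.846) × 0.286 = 0.81 SD
- at 0.0167: (2.438 + 0.846) × 0.286 = 0.94 SD
- at 0.00625: (2.797 + 0.846) × 0.286 = 1.04 SD

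**The case against.** The strongest reply is that the SAP may describe a sound analysis too briefly. One merged mask may have been used, Hypothesis 1.1 can be read as requiring all three regions, and the ANOVA may have come first. Aim 1 is also to characterise and compare brain responses in a mechanistic study. Much of this stands: under one mask with one test, or an all-three rule, the error rate is 5% or less. But the text supports these readings no better than the others, and the SAP does attach significance thresholds to a declared primary outcome.

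The model is also simple. Small-volume correction searches voxels or clusters within a mask, and the relevant correlation is between the results of those searches. This limits how exactly any percentage can be taken. It does not remove the excess over 5%, which holds under the per-region, any-one reading for every correlation below 1 in the model.

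Four stronger inferences are tempting, and the documents do not support them:

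- That this trial's false-positive rate is 22-25%, or 34%. Those are points in an assumed range under one reading of the SAP.
- That the region list was widened after the data were seen. The past tense and final numbers mean the SAP cannot show the list was fixed beforehand; they do not show the opposite.
- That requiring the ANOVA gives no protection because real acupuncture may work alone. Hypothesis 1.1 predicts that both VGAIT and real acupuncture raise the three regions. With a shift in one region the rate is 17/13/7%, well below the ungated two-sided 34/25/12%.
- That the p < 0.005 for the listed regions is uncorrected. The sentence can also be read as a height threshold used with small-volume correction, or as itself small-volume corrected.

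**Conclusion.** The point holds as a specification gap in the primary analysis. The omissions are plain from the SAP, and nothing in the protocol fills them. The size of the consequence is conditional. With per-region correction, any one region counting and no ANOVA required first, the error rate for V-GAIT against its control is about 34% to 11% as the assumed correlation goes from 0 to 0.9. Restricting to the three hypothesised regions but counting any one still leaves about 14% to 8%. Requiring the ANOVA helps, but at low or moderate correlation it leaves the eight-region rate well above 5%.

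Confidence is high in the omission and limited in the exact inflation. It should be fixed before any regional result is presented as confirmatory.

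**What to change.** 1. State whether small-volume correction was per region or over a combined mask, which contrast is primary and in which direction, and what p < 0.005 means for the listed regions.
2. For V-GAIT against V-GAIT control, treat AI, MCC/dACC and PAG as confirmatory and state the success rule. If any one suffices, use Holm across the three (0.0167 for the smallest p) or one small-volume correction over a combined mask of the three. If all three are required, test each at 0.05. Do not rely on the ANOVA for multiplicity.
3. Report the other listed regions and the search outside them as exploratory for this contrast, or correct over all eight (0.00625). Report S1 for real acupuncture against VGAIT as its own hypothesis.
4. Name the masks. Disclose that masks chosen after analysis are not prespecified, and show whole-insula and whole-cingulate results as a sensitivity analysis.

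Other multiplicity schemes would also be defensible; this one uses the protocol's own regions. The cost is wording and re-thresholding of existing maps, with no new data. Under an any-one rule the detectable difference per region rises from 0.81 to 0.94 SD, or to 1.04 SD over eight. Under an all-three rule, if every region truly differs by 0.81 SD, power is about 53% (independent) to 73% (correlation 0.9), against 96% to 76% for any of three at 0.0167 (normal approximation).
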